**AND**

2. Still on broad spectrum antibiotic therapy after 48-96 hours.
  - a. Broad spectrum antibiotics will be defined by agent as described in the rank list below (Table 1). Any agent in the 2, 3, or 4 rank categories will be considered broad spectrum.

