**Table 3. DETOURS Desirability of Outcome Ranking (DOOR) Outcome**

Outcome	Rank
Alive	1
Readmission, relapse of suspected sepsis, C. difficile infection, OR deep venous thrombosis	2
≥2 of items in Rank 2 above	3
Subsequent ICU Admission OR hemodialysis	4
Subsequent ICU Admission AND hemodialysis	5

Death	6
-------	---

*Secondary endpoints:*

- 1) DOOR/RADAR, according to criteria developed in DETOURS-Retro (Pro00076818; Table 3). See Section 7 for definitions of these and other outcomes.
- 2) Safety outcomes potentially related to antibiotic treatments:
  - a. Individual clinical outcome components in the DOOR (Table 3)
  - b. Number of hospital days within 30-days post-randomization
  - c. Re-initiation of antibiotic therapy after >48 hours of no antibiotics within 30-days post-randomization
  - d. Need for new PICC line insertion within 30-days post-randomization
  - e. Central line days within 30-days post-randomization.
- 3) Process indicators:
  - a. Percent of eligible patients with antibiotic de-escalation by day 5, according to an electronic definition of de-escalation
  - b. Of those patients eligible for assessment of de-escalation per the Safety Checklist:
    - i. Number of eligible patients in whom the safety screen was applied.
    - ii. Number patients the safety screen excluded from the opt-out procedure
    - iii. Number of eligible patients in whom the opt-out procedure was employed
    - iv. Number of eligible patients in whom the prescriber chose to opt-out
      1. Prescriber type (e.g. physician, APC, trainee, specialty service consultant (e.g. infectious diseases))
      2. Prescribers' reported rationale for opting out
  - c. Percent of subjects who received an infectious disease consultation after implementation of the Opt-Out
- 4) Days of therapy for specific sub-groups of patients, including patients whose physicians elected to opt-out of the intervention, and sub-groups of hospitals (e.g., community vs. tertiary care hospitals).
- 5) Total days of therapy for each patient, defined as a sum of inpatient days of therapy and projected outpatient days of therapy, as per discharge prescriptions.
- 6) Length of therapy (LOT), defined as the number of days during which the patient receives one or more antibiotics. Repeat primary outcome and secondary outcomes #4 and #5 with LOT.

*Additional Descriptive Data*

We will obtain the following data from each of the patients eligible for the Opt-out protocol:

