## 7 ASSESSMENT OF SAFETY

All randomized patients will undergo safety evaluation.

1. Specifications of safety parameters –Data will be collected on the adverse outcomes described in the Desirability of Outcome Ranking (DOOR) in Table 3 and three other safety outcomes:
  - a. C. difficile infection (CDI) – positive *C. difficile* stool test during the 30 days following randomization. Results from either PCR or ELISA tests are acceptable
  - b. Clinically significant deep venous thrombosis (DVT) – diagnosis of a new DVT during the 30 days following randomization that requires anticoagulation. A radiographic finding (via ultrasound, CT, or MRI) will be required for this diagnosis.
  - c. Readmission – return to the hospital within 30 days of hospital discharge
  - d. Relapse of suspected sepsis – restart or escalation of antibiotic therapy coupled with repeat blood cultures (+/- 24 hours of changed in antibiotic therapy) during the 30 days following randomization.
  - e. Acute kidney injury requiring hemodialysis – new onset acute kidney injury requiring 1 or more hemodialysis sessions during the 30 days following randomization.
  - f. Transfer to Intensive Care Unit (ICU) – admission or transfer to any intensive care unit within 30 days of randomization.
  - g. Death – within 30 days of randomization.
  - h. Number of hospital days (Length of Stay) starting on the day of randomization and up to 30 days post randomization.
  - i. Re-initiation of antibiotic therapy after >48 hours of no antibiotics within 30 days of randomization.
  - j. Need for new PICC line insertion within the 30 days of randomization.
2. Methods and timing for assessing, recording, and analyzing safety parameters – Local study personnel will be responsible for assessing and recording safety parameters. Duke study personnel will be responsible for monitoring safety through interaction with study site PIs and the Independent Monitor.
3. Guidelines for determining causality – causality will not be assessed, as the DOOR outcome is intended to reflect global patient outcomes.
4. Reporting procedures (for AE) – all safety parameters will be entered into the REDCap database. Data on safety parameters will be reviewed by the Independent Monitor and discussed with the central study team.

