## MANAGEMENT OF RISKS TO SUBJECTS

### Expected AEs

Expected AEs associated with hospitalization, the receipt of antibiotics, treatment of infection and the DETOURS protocol include:

- C. difficile infection (CDI) – positive *C. difficile* stool test during the 30 days following randomization. Results from either PCR or ELISA tests are acceptable
- Clinically significant deep venous thrombosis (DVT) – diagnosis of a new DVT during the 30 days following randomization that requires anticoagulation. A radiographic finding (via ultrasound, CT, or MRI) will be required for this diagnosis.
- Readmission – return to the hospital within 30 days of hospital discharge

- Relapse of suspected sepsis – restart or escalation of antibiotic therapy coupled with repeat blood cultures (+/- 24 hours of changed in antibiotic therapy) during the 30 days following randomization.
- Acute kidney injury requiring hemodialysis – new onset acute kidney injury requiring 1 or more hemodialysis sessions during the 30 days following randomization.
- Transfer to Intensive Care Unit (ICU) – admission or transfer to any intensive care unit within 30 days of randomization.
- Death – within 30 days of randomization.
- Number of hospital days (Length of Stay) starting on the day of randomization and up to 30 days post randomization.
- Re-initiation of antibiotic therapy after >48 hours of no antibiotics within 30 days of randomization.
- Need for new PICC line insertion within the 30 days of randomization.

Causality of SAEs to the study protocol will not be assessed, as the study monitoring plan follows global patient outcomes due to antibiotic exposures. Thus, effects from routine care and the study protocol are difficult to attribute because this is a quality improvement protocol.

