**Table for Review by the Internal Monitor**

	Intervention	Control	Total
C. difficile infection, No. (%)			
Deep venous thrombosis, No. (%)			
Readmission, No. (%)			
Sepsis relapse, No. (%)			
Acute kidney injury requiring hemodialysis, No. (%)			
ICU transfer, No. (%)			
Death, No. (%)			
Hospital days (Length of stay), median, interquartile range			
Re-initiation of antibiotic therapy, No. (%)			
New PICC line insertion, No. (%)			

Communication plans for interaction between the IM and the study team will be primarily through email. The IM will respond with 7 business days of receipt of the safety data report with

their assessment. If further discussion is needed, then phone discussion within 3 business days will be arranged.

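### Relapse and re-initiation are scored through a change in antibiotic therapy, which the intervention itself alters, and an early reversal of a protocol stop without repeat blood cultures is counted in neither

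*Protocol*

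**What the plan says.** Section 7, item 1.d, and the expected adverse events in Appendix 4 define relapse as "restart or escalation of antibiotic therapy coupled with repeat blood cultures", with the cultures taken within 24 hours either side of the change and the event falling in the 30 days after randomization. Table 3 in Section 5.1 places it in DOOR rank 2 ("Readmission, relapse of suspected sepsis", with *C. difficile* infection and deep venous thrombosis). Two or more of these items give rank 3. DOOR/RADAR is the first secondary endpoint.

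Re-initiation is secondary safety endpoint 2.c, worded "Re-initiation of antibiotic therapy after >48 hours of no antibiotics within 30-days post-randomization". Section 7, item 1.i, and Appendix 4 set the same condition. The Independent Monitor's table in Appendix 4 has a row for each outcome by arm, including "Re-initiation of antibiotic therapy, No" with a percentage.

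The inclusion criteria in Section 4.1.2 require that the patient is "Still on broad spectrum antibiotic therapy after 48-96 hours". Step 4 of the opt-out protocol then stops antibiotics in the intervention arm unless the treating team opts out, while control patients receive standard care. Section 5.1 states that there is no blinding of study personnel after randomization.

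**The concern.** Both outcomes need a change in antibiotic therapy before they can be scored, and randomization changes antibiotic therapy. The same clinical episode can therefore be classified differently according to whether the patient is on or off antibiotics when it occurs.

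The 48-hour condition raises a separate problem. A stop made under the protocol and reversed soon afterwards is the most direct sign that the treating team came to regard it as wrong. Stopping antibiotics inappropriately is the risk that Section 2.3.1 itself names. Such a reversal is never a re-initiation, and it is a relapse only if blood cultures were repeated.

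At stake are the relapse component of DOOR, the re-initiation endpoint, and two rows that the Independent Monitor reads at 10%, 25% and 50% of enrollment when looking for differences between arms.

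**Working it through.** The protocol gives no figure for this point, so the check is first a reading of the definitions and then an illustration with assumed inputs.

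**Classification under Section 7**

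| Course after randomization | Repeat blood cultures within 24 h of the change | Relapse (DOOR rank 2) | Re-initiation |
|---|---|---|---|
| Off antibiotics, restarted after more than 48 h | yes | yes | yes |
| Off antibiotics, restarted after more than 48 h | no | no | yes |
| Off antibiotics, restarted at or before 48 h | yes | yes | no |
| Off antibiotics, restarted at or before 48 h | no | **no** | **no** |
| On antibiotics, escalated | yes | yes | no |
| On antibiotics, re-cultured, regimen unchanged | cultures taken, but no change | **no** | **no** |

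The two rows in bold are the gaps. Two facts follow from the wording alone:
- Re-initiation cannot be scored while a patient is still on antibiotics.
- Off antibiotics, a restart of any spectrum meets the drug part of relapse. On antibiotics only an escalation does, and the protocol does not define that term.

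**Illustration of the relapse asymmetry (all inputs assumed)**

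- d: true risk of deterioration, the same in both arms, 5% to 15%.
- f: share of patients off antibiotics when they deteriorate, 30% or 50% in intervention against 10% or 20% in control.
- q_off: probability that a deterioration off antibiotics leads to restart plus cultures, 0.9.
- q_on: probability that a deterioration on antibiotics leads to escalation plus cultures, 0.9, 0.7 or 0.5.

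Counted risk in an arm = d × [f × q_off + (1 − f) × q_on].

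Difference between arms = d × (f_int − f_ctl) × (q_off − q_on).

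With d = 10%, f = 50% against 10%, and q_on = 0.5:
- intervention: 0.10 × (0.5 × 0.9 + 0.5 × 0.5) = 7.0%
- control: 0.10 × (0.1 × 0.9 + 0.9 × 0.5) = 5.4%
- difference 1.6 points, ratio 1.30; at 762/2 = 381 per arm, about 27 against 21 events.

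Over three pairs of f (30% against 10%, 50% against 10%, 50% against 20%) and d from 5% to 15%:

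| q_on | Ratio of counted relapse | Difference (points) |
|---|---|---|
| 0.9 | 1.00 | 0 |
| 0.7 | 1.06 to 1.11 | 0.2 to 1.2 |
| 0.5 | 1.15 to 1.30 | 0.4 to 2.4 |

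The spurious difference vanishes when deterioration is acted on equally on and off therapy, and it would reverse sign if q_on exceeded q_off. At the monitor's first review (10% of 762 is 76, about 38 per arm) the 1.6-point difference is 0.016 × 38 = 0.6 of an event.

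**The case against.** The case against making much of this is substantial.

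- Relapse includes escalation, so deterioration on therapy can be scored. The asymmetry needs a patient who is re-cultured and left on the same regimen, and the protocol does not say how often that happens. This stands, and it is why the asymmetry is called partial.
- Relapse has no minimum antibiotic-free interval, so an early restart with cultures reaches DOOR rank 2. A reader might infer that all failures in the first two days after stopping are missed. They are not. Only early restarts without repeat blood cultures are, and some of those may be a prescriber's change of mind rather than clinical failure. Restarts in the index stay also add to the primary DOT count.
- Death, ICU transfer, hemodialysis, deep venous thrombosis and readmission are not defined by an antibiotic change and are reported separately. Safety outcomes receive summary statistics, and the monitor's review has no numerical threshold. This stands and limits the consequences.
- A reader might try to size the re-initiation problem by exposure. With an assumed 5-day stay and a 2% restart risk per antibiotic-free day, a patient stopped on day 0 would score (5 − 2) × 2% = 6% and one treated to discharge 0%. That does not measure bias. A patient never off antibiotics has no restart to miss, so the gap is a real difference in restarts. It also compares two extreme patients rather than two arms, and it ignores that control patients finish therapy within the 30 days.
- It may seem natural to give re-initiation per patient or per day off antibiotics. That denominator is formed after randomization by the intervention itself, so the groups compared would no longer be the randomized ones. The percentage of all randomized fits the intent-to-treat population in Section 9.4.1.

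None of this brings the two uncounted situations into any outcome defined by restart or relapse.

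**Conclusion.** The point holds in a limited form. Relapse and re-initiation depend on antibiotic status, which the intervention changes by default in unblinded care. Re-cultured deterioration on an unchanged regimen is not scored. A protocol stop reversed at or before 48 hours without repeat blood cultures appears in neither outcome.

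These statements follow from the definitions. The size does not: the ratios of 1.00 to 1.30 rest entirely on assumed inputs. A reader might infer that the arm comparison is biased against the intervention. The documents do not support a net direction, because easier scoring off antibiotics works against the intervention while leaving out early reversals works in its favor. The effect on DOOR is confined to one of the four rank 2 items, and the primary endpoint's definition is not affected. This is worth correcting, but it does not undermine the trial.

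**What to change.** Keep the present definitions and add the following in Sections 5.1 and 7 and Appendix 4:

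1. From eMAR, count restarts after any antibiotic-free calendar day (the calendar day is already the unit for DOT). Show those within 48 hours and those after 48 hours separately, by arm, as No. (%) of all randomized, in the analysis and in the monitor's table. Do not compare arms on a denominator of patients or days off antibiotics.
2. Add a sensitivity version of relapse, and of DOOR, that counts repeat blood cultures from the day after randomization whether or not antibiotics changed. Label it as less dependent on antibiotic status but not free of it, because in unblinded care the decision to culture can itself depend on whether antibiotics were stopped.

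The cost is programming on eMAR and laboratory extracts that Section 5.1 already plans, plus a few table rows. The downside is that some short dosing gaps and routine follow-up cultures will be counted in the added versions. The calendar-day rule also cannot detect a gap of 24 hours or less, and between 24 and 48 hours it detects only gaps that contain a whole calendar day.

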### Independent Monitor

As outlined above, we believe the study intervention qualifies as quality improvement activity, and offers no additional risk than routine medical care. However, some clinicians may worry that cessation of antibiotics, even in the low risk population which DETOURS study screening processes select, could result in negative clinical outcomes for patients who had a clinically

ambiguous presentation or unconfirmed infection at the 48-96-hour time point. Thus, we plan to use an Independent Monitor.

The independent Monitor will be a qualified and objective individual not directly involved with the design and conduct of the study. This individual will not be an employee of any participating institution or the study sponsor. This individual will have no conflict of interest related to assessment of the study, will have adequate experience and expertise in conduct of clinical trials, statistics, and antimicrobial stewardship. Full description of the Independent Monitor plan is provided in Appendix D.

The independent monitor will focus on safety outcomes and not the primary outcome of antibiotic use. No statistical testing alpha value will be pre-assigned to indicate the need to halt or adjust the study protocol. No hypothesis testing is planned. Instead, an expert review of patient-level outcomes will be performed to ensure no concerning differences in safety events between the two arms are emerging.

## **8 CLINICAL MONITORING**

ICH E6 states that the purpose of monitoring is to ensure the rights of subjects, obtain accurate data, and conduct trial in accordance with protocol and applicable regulations. Routine procedures in our study group and through the research infrastructure at DUHS ensure the qualification of hospital personnel to conduct the trial, regulatory requirements (e.g. IRB review), protocol training, data quality monitoring procedures, hospital data completion expectations (e.g. completeness, frequency, etc.). Rights of subjects will be maintained at all times as outlined in the Privacy section.

## 9 STATISTICAL CONSIDERATIONS

### 9.1 Design and Sample Size Considerations

The study is designed as a multicenter randomized controlled trial to test the primary hypothesis that use of an opt-out protocol in appropriate patients will decrease unnecessary antimicrobial utilization. Power calculations were re-run after the initiation of the study (v.4 of protocol) because of findings from a recently completed study by our group and others examining the importance and impact of post-discharge antimicrobial therapy on utilization metrics. In essence, estimated post-discharge DOT were added to estimated inpatient DOT, and power calculations were re-run.

#### *Power calculations*

Power was calculated using a simulation study. First, we evaluated 6 months of data from three hospitals in our network, including 1 tertiary care center and 2 community hospitals. Eligible patients were defined as follows:

1. Blood cultures drawn and negative
  - a. Except 1 of 2 common skin flora
2. Broad antibiotics at 2-3 days after time of blood culture draw
3. We will define the 2nd calendar day after date of blood culture draw as “screen date”
4. The patient is eligible if they received broad antibiotic on either the screen date (day 2) or the day after (day 3).
5. Located on an inpatient medical, surgical, telemetry, or medical/surgical ward on screen date

The main outcome of interest was DOT after screen date, counting inpatient days of therapy occurring screen date + 1 until discharge, and adding post-discharge DOT as defined in electronic prescriptions upon hospital discharge. Table 4 outlines total enrollment assumptions at study hospitals.

A negative binomial regression model was fitted to the admission-level data on DOT. No difference in DOT was found between different types of wards (Medical/Surgical, Surgical, Medical and Telemetry;  $p=0.39$ ) so the final model included intercept only. Hospital was included as a random effect in the model. Mean DOT was estimated as  $\exp(\text{Intercept}) = \exp(2.43) = 11.4$  days, negative binomial scale as 1.68 and variance of the hospital random effect as 0.12.

**Table 4.** Total enrollment assumptions in 10 study hospitals.

		Enrollment/ month	Months in study	Enrollment estimate
Harvard	Academic	10	15	150
Duke	Academic	10	18	180
Penn	Academic	10	18	180
Presbyterian	Community	2	18	36
Wilson	Community	2	18	36
Iredell	Community	2	18	36
SRMC	Community	2	18	36
Fayette	Community	2	18	36
ATL	Community	2	18	36
Newnan	Community	2	18	36
			total	762

Power was estimated using a simulation study with 500 repetitions. Based on the above assumptions, DOT per admission in the standard care arm were generated in each hospital from a negative binomial distribution with mean=(11.4+hospital effect) and scale=1.68, where hospital effect was generated from a normal distribution with mean 0 and variance 0.12. DOT in the opt-out arm were generated from the same model with the mean=(eff\*11.4+hospital effect), where reduction in mean DOT parameter “eff” ranged in values from 0.9 to 0.6 (i.e. 10%-40% reduction).

The data analysis was performed using GEE negative binomial regression with treatment as the only covariate, hospital as the cluster variable and assuming compound symmetry covariance structure within the clusters.

With these assumptions, power ranged from 28% for 10% reduction to >99% power for 40% reduction in mean DOT.

Decrease in mean DOT	Power
10%	28%
20%	66%
25%	87%
30%	96%
40%	>99%

Using these calculations, target enrollment was set at n=762, giving us 87% power to calculate a 25% decrease in mean DOT. Power for the secondary outcome (DOOR/RADAR) will be calculated after SA3 and 4 are completed.

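### The power simulation puts a log-scale hospital variance on a mean in days, and its 87% fits a test that does not hold 5%; about 83–84% is supportable with hospital in the model

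*Protocol*

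**What the plan says.** All of this is in the protocol, section 9.1 (Power calculations), unless noted.

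- Planning model: "A negative binomial regression model was fitted to the admission-level data on DOT", with hospital as a random effect. The mean is obtained by exponentiating the intercept, exp(2.43) = 11.4 days. The other estimates are "negative binomial scale as 1.68 and variance of the hospital random effect as 0.12".
- Simulation: control-arm DOT has "mean=(11.4+hospital effect) and scale=1.68, where hospital effect was generated from a normal distribution with mean 0 and variance 0.12". The opt-out arm uses eff × 11.4 plus the same kind of hospital effect. "Power was estimated using a simulation study with 500 repetitions".
- Hospitals: Table 4 gives 150, 180 and 180 patients at three academic sites and 36 at each of seven community sites, 762 in all.
- Analysis of the simulated data: "GEE negative binomial regression with treatment as the only covariate, hospital as the cluster variable and assuming compound symmetry covariance structure within the clusters". Section 9.4.1 plans the same model for the primary analysis.
- Result: "power ranged from 28% for 10% reduction to >99% power for 40% reduction in mean DOT", with 66%, 87% and 96% at 20%, 25% and 30%. The target is 762, "giving us 87% power to calculate a 25% decrease in mean DOT".
- Section 9.2: randomisation is 1:1, stratified by hospital.

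Neither section 9.1 nor section 9.4.1 states alpha, sidedness or the type of standard error.

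**The concern.** Two things do not fit together.

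First, a variance from a model whose mean is exp(intercept) lives on the log scale. Adding it to 11.4 days treats 0.12 as days squared and removes nearly all the between-hospital variation that the planning data showed.

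Second, the 10% row is too high. With 381 patients per arm and a dispersion of 1.68, a two-sided 5% test should have about 19% power there, not 28%. Excess power at a small effect is the usual sign of a test that also rejects too often when there is no effect. A cluster-robust GEE with 10 clusters of very unequal size is a well-known way to get such a test.

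Target enrolment rests on the 87%. The same model is planned for the primary analysis, so whatever inflated the simulated power could also inflate the type I error of the trial's main result.

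**Working it through.** **Inputs.** Control mean 11.4; dispersion 1.68, with variance μ + 1.68μ²; hospital variance 0.12; Table 4 sizes; 1:1 within hospital. Two-sided 5% is an assumption. Reading 1.68 as the inverse of the dispersion would give 99.7% power at a 25% reduction, so that reading is ruled out.

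**Step 1. Scale of the hospital effect.**
- As simulated: SD = √0.12 = 0.35 day; 95% of hospital means lie in 11.4 ± 1.96 × 0.346, or 10.7 to 12.1 days.
- On the log scale: 11.4 × exp(±1.96 × 0.346) gives 5.8 to 22.5 days; SD = 11.4 × exp(0.06) × √(exp(0.12) − 1) = 4.3 days.

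**Step 2. Closed-form benchmark, two-sided 5%.** SE(log ratio) = √[(1/11.4 + 1.68)/381 + (1/(11.4·eff) + 1.68)/381]. At eff = 0.75 this is 0.0967, so z = 0.2877/0.0967 = 2.97 and power = Φ(2.97 − 1.96) = 84.5%. The 10%, 20% and 30% rows come to 19%, 64% and 96%.

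**Step 3. Reproducing the plan's table.** The documented process was simulated (effect in days, exchangeable treatment-only GEE, critical value 1.96, 10,000 runs per row):

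| Reduction | Stated | Uncorrected sandwich SE | Model-based SE |
|---|---|---|---|
| 10% | 28% | 29.8% | 19.4% |
| 20% | 66% | 70.4% | 63.3% |
| 25% | 87% | 86.9% | 84.3% |
| 30% | 96% | 96.1% | 95.6% |
| No effect | not given | 12.2% | 5.3% |

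Distance of the stated figures from each column, in Monte Carlo SEs of a 500-run simulation:
- Sandwich: −0.9, −2.1, 0.1 and −0.1 at 10/20/25/30%; sum of squares 5.4.
- Model-based: 4.9, 1.3, 1.7 and 0.5; sum of squares 28.2.

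For the 10% row: (28 − 19.4)/(100 × √(0.194 × 0.806/500)) = 8.6/1.77 = 4.9. A one-sided 5% test gives 29/75/91/98%. It fits the 10% row but misses the 20% row by (66 − 74.7)/1.94 = −4.5 SEs.

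**Step 4. Changing only the scale** (mean = 11.4 × eff × exp(b), b ~ N(0, 0.12)), at a 25% reduction:
- Sandwich: about 87% to 86%, while its rejection rate under no effect rises from 12.2% to 13.5%. Across separate simulations of the log-scale case that rate reached about 15%.
- Model-based: about 85% to 82%.
- Hospital as a fixed effect: 84.1% to 83.6%.
- Tests calibrated to exactly 5%: 84.4% to 80.8% (model-based) and 71.3% to 68.0% (sandwich).

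The scale error alone is therefore worth at most about 4 points.

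**Step 5. Log scale and about 5% size together**, 25% reduction, n=762:

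| Analysis | Power |
|---|---|
| Hospital as fixed effect (type I error 5.4%) | 83–84% |
| Treatment-only GEE, model-based SE (type I error 5.4%) | 80–82% |
| Treatment-only GEE, cluster sandwich corrected or calibrated to hold 5% | 66–71% |

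No variant that holds 5% reaches 87%.

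**The case against.** The case on the other side is substantial in four respects.

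- **The 87% is not a slip of arithmetic.** It reproduces from the documented inputs (86.9%). It also lies only about 1.6 Monte Carlo SEs above the closed form: (87 − 84.5)/(100 × √(0.845 × 0.155/500)) = 2.5/1.62. This stands.
- **The scale error does little by itself.** Stratified randomisation lets most of the hospital effect cancel. This stands too. A reader might infer from the wrong scale that the trial is seriously underpowered; the figures do not support that.
- **The sandwich error is inferred.** The protocol names no standard error, alpha or sidedness, and the inference rests mainly on the 10% row. At 20% the stated 66% is nearer the model-based figure. So the table is more consistent with an uncorrected sandwich, but that is not proven. A reader might go further and conclude that the primary analysis will have a 12–15% type I error. The document does not support that: section 9.4.1 never says the errors will be robust or uncorrected, and it leaves full details to the SAP.
- **The 0.12 comes from three hospitals**, so the 5.8 to 22.5 day range is itself uncertain. True, but it remains the sponsor's own estimate, and the simulation did not use it as estimated.

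The objection leaves two points standing. The scale mismatch is on the page. The 28% is also hard to reconcile with a two-sided 5% test, and a later SAP would not correct the power statement printed here.

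**Conclusion.** The point holds in limited form and should be fixed, but it does not undermine the trial's size. The hospital variance is used on the wrong scale, at a cost of about 1 to 4 points. Under an assumed two-sided 5% level, the stated table fits best with a test that rejects about 12–15% of the time under no effect. At n=762, valid power for a 25% reduction is about 83–84% with hospital in the model, or 80–82% for the treatment-only GEE with model-based errors. It is about 66–71% if the cluster sandwich is kept and made to hold 5%. For a 10% reduction it is about 19–20%, not 28%.

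Confidence is high on the scale mismatch and moderate on the standard-error type. The figures take the sponsor's mean, dispersion and hospital variance as given. The more important consequence is that the primary-analysis model should be fixed in a form known to hold its level with 10 hospitals.

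**What to change.** 1. Re-run the simulation with mean = 11.4 × eff × exp(b), b ~ N(0, 0.12), and add a row for no effect so that type I error is shown beside power.
2. State alpha, sidedness and the type of standard error in sections 9.1 and 9.4.1.
3. Make the primary model a negative binomial regression with hospital, the stratification factor, as a fixed effect and with model-based or patient-level robust errors. Use the same model in the simulation.
4. Restate power at n=762 as about 83–84% for a 25% reduction and about 19–20% for 10%.
5. If the treatment-only GEE is kept, quote about 80–82% with model-based errors, or about 66–71% with a cluster sandwich corrected to hold 5%.

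The cost is a few lines of simulation code, a revised table and two amended paragraphs. The stated power falls by about 3 to 4 points on the recommended route (87% to 83–84%), and no extra patients are needed.
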